5.1.1.1 Tumor Lysis Syndrome

The available data suggest that in patients with non-CLL, with the exception of those with mantle cell lymphoma, the risk of TLS is low. Due to different biology between ER+ breast cancer and hematological malignancies, the risk of TLS is considered to be very low in patients with ER+ breast cancer. Therefore, TLS prophylaxis is not recommended by any of the international guidelines for patients with ER+ breast cancer, even in those patients who have developed visceral crisis and are receiving chemotherapy.

The target population in this trial is considered to have low disease burden compared with patients who have visceral crisis and therefore TLS risk is negligible. Nevertheless, patients should be advised to remain well hydrated for the first week of study drug administration. Although not mandatory, at the discretion of the investigator, a prophylactic oral agent (e.g., allopurinol 300 mg QD) may be initiated in patients who are deemed to be at the risk of TLS in order to reduce the uric acid level. Laboratory values obtained before the dose of venetoclax are to be used to determine whether a patient developed a change related to TLS. Laboratory results of the 24-hour postdose must be reviewed before receiving the dose of venetoclax for that day. Patients who develop electrolyte changes suggestive of TLS should undergo aggressive management and further monitoring per [Appendix 9](#).

Patients with TLS should be treated as per institutional practice and local guidelines, including correction of electrolyte abnormalities and monitoring of renal function and fluid balance. Recommendations for initial management of electrolyte imbalances and prevention of tumor lysis syndrome are provided in [Appendix 8](#). In some cases, dialysis may be indicated. Guidelines for defining TLS are provided in [Appendix 9](#).

To evaluate any possible risk of TLS with venetoclax in patients with ER+ breast cancer, the first 10 patients enrolled into each arm of the study will each have a sample collected for a serum chemistry panel 24 hours after the first dose of study drug. The IMC will convene after 5 patients are enrolled in each arm to review the chemistry panel results and establish a management plan for TLS if an increased risk is identified, if needed.

5.1.1.2 Neutropenia

Neutropenia is an important identified risk for venetoclax. Clinical data from the oncology studies suggest that the neutropenia adverse events are observed among subjects who receive venetoclax as a single agent or in combination with other therapeutic agents, with higher frequency observed in some combination studies. Serious adverse events of neutropenia or neutropenia events that lead to discontinuations are few across the entire venetoclax oncology program. Neutropenia management guidelines are provided in [Table 3](#). Granulocyte colony stimulating factors are permitted according to local practice, and patients will be monitored and treated promptly in case of infection.

5.1.1.3 Infections

Infections have been reported in oncology clinical studies; however, these events are confounded by the underlying disease, comorbidities, and other immunosuppressive medications. To date, no clear relationship has been noted between serious infectious events and neutropenia. The types of infectious events observed generally have been consistent with those anticipated in the elderly population of heavily pretreated patients with hematologic malignancies and are similar across all indications.

Patients in this study will be closely monitored for infections and prompt therapy will be instituted as necessary as per local SOC.

5.1.1.4 Other Hematological Effects

Anemia has been reported across oncology studies investigating venetoclax, with a higher frequency in some studies in which venetoclax is combined with other reference therapies; however, most of the events were non-serious and confounded by disease factors and prior therapies.

Thrombocytopenia adverse events have been reported in oncology studies investigating venetoclax, with a higher frequency in those studies in which venetoclax was combined with other chemotherapeutic agents. However, most of the events were non-serious and assessment of these events is confounded by the patients' underlying hematologic malignancy disease state, prior therapies, and preexisting thrombocytopenia, including autoimmune thrombocytopenia in several patients.

Lymphopenia has been observed in nonclinical studies and in the Phase I clinical study conducted in heavily pretreated patients with CLL and NHL. While opportunistic infections have been reported in the clinical program, data are confounded by the patients' underlying disease and prior therapies. Patients in this study who develop lymphopenia are potentially at risk for atypical infections. As such, prophylaxis against varicella zoster virus and *Pneumocystis jiroveci* pneumonia should be considered and implemented (if applicable) as per local institutional practice, although some guidance is provided in [Appendix 7](#).

5.1.1.5 Reproductive System Effects and Pregnancy

This study enrolls only female patients. The effect of BCL-2 inhibition on pregnancy has not been fully characterized. In animal studies, venetoclax resulted in increased post-implantation loss, and decreased fetal body weights were observed in the mouse embryo-fetal development study at the highest dosage administered. Venetoclax was not teratogenic.

Two human pregnancies have been reported in the clinical program with venetoclax so far, including one pregnancy of a partner; in both cases, a live infant with no neonatal complication, congenital anomalies, or birth defects was delivered.

In nonclinical studies, both venetoclax and fulvestrant have shown a potential to cause reproductive and embryo-fetal developmental toxicities as single agents. Therefore, there is the potential for this combination to cause overlapping or additional reproductive and embryo-fetal toxicities than the individual molecules. Consequently, both venetoclax and fulvestrant should not be administered to pregnant women, and they must be discontinued if a patient becomes pregnant. Additionally, patients are advised to remain abstinent (i.e., refrain from heterosexual intercourse) or use non-hormonal contraceptive methods with a failure rate of < 1% per year during the treatment period and for *up to 2 years after the last dose of study drug (or based on the local prescribing information for fulvestrant)*. Please refer to Section 4.1.1 for further details on study eligibility and contraceptive requirements for patients.

5.1.1.6 Treatment-Emergent Malignancies (Second Primary Malignancies)

Events of second primary malignancies have been reported across the venetoclax hematologic oncology program. However, no causal association with the venetoclax administration has been confirmed, and no pattern has been observed. The overall observed incidence rate of malignancy in the venetoclax clinical trial programs were comparable to that reported in the general population. The second primary malignancies will be closely monitored in this study.

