3.3 END OF STUDY AND LENGTH OF STUDY

The study duration will be the time from screening of the first patient through 2 years after the last patient is enrolled, or all patients in the study have withdrawn consent or died, or if the study is prematurely terminated by the Sponsor, whichever occurs first. With enrollment anticipated to last approximately 18 months, the total length of the study is expected to be approximately 43 months.

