5.2.3 Adverse Events of Special Interest (Immediately Reportable to the Sponsor)

Adverse events of special interest are required to be reported by the investigator to the Sponsor immediately (i.e., no more than 24 hours after learning of the event; see Section 5.4.2 for reporting instructions). Adverse events of special interest for this study are as follows:

- Cases of potential drug-induced liver injury that include an elevated ALT or AST in combination with either an elevated bilirubin or clinical jaundice, as defined by Hy's Law (see Section 5.3.5.7)
- Suspected transmission of an infectious agent by the study drug, as defined below:

Any organism, virus, or infectious particle (e.g., prion protein transmitting transmissible spongiform encephalopathy), pathogenic or non-pathogenic, is considered an infectious agent. A transmission of an infectious agent may be suspected from clinical symptoms or laboratory findings that indicate an infection in a patient exposed to a medicinal product. This term applies only when a contamination of the study drug is suspected.
- TLS

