5.3.1 Adverse Event Reporting Period

Investigators will seek information on adverse events at each patient contact. All adverse events, whether reported by the patient or noted by study personnel, will be recorded in the patient's medical record and on the Adverse Event eCRF.

After informed consent has been obtained but prior to initiation of study drug, only serious adverse events caused by a protocol-mandated intervention (e.g., invasive procedures such as biopsies, discontinuation of medications) should be reported (see Section 5.4.2 for instructions for reporting serious adverse events).

After initiation of study drug, all adverse events will be reported through 28 days after the last dose of study drug (venetoclax or fulvestrant, whichever is later). After this period, investigators should report any deaths, serious adverse events, or other adverse events of concern that are believed to be related to prior study drug treatment as prescribed in Section 5.6.

Instructions for reporting adverse events that occur after the adverse event reporting period are provided in Section 5.6.

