5.3.4 Assessment of Causality of Adverse Events

Investigators should use their knowledge of the patient, the circumstances surrounding the event, and an evaluation of any potential alternative causes to determine whether an adverse event is considered to be related to the study drug, indicating "yes" or "no" accordingly. The following guidance should be taken into consideration (see also [Table 5](#)):

- Temporal relationship of event onset to the initiation of study drug
- Course of the event, with special consideration of the effects of dose reduction, discontinuation of study drug, or reintroduction of study drug (as applicable)
- Known association of the event with the study drug or with similar treatments
- Known association of the event with the disease under study
- Presence of risk factors in the patient or use of concomitant medications known to increase the occurrence of the event
- Presence of non-treatment-related factors that are known to be associated with the occurrence of the event

Table 5 Causal Attribution Guidance

Is the adverse event suspected to be caused by the study drug on the basis of facts, evidence, science-based rationales, and clinical judgment?	
YES	There is a plausible temporal relationship between the onset of the adverse event and administration of the study drug, and the adverse event cannot be readily explained by the patient's clinical state, intercurrent illness, or concomitant therapies; and/or the adverse event follows a known pattern of response to the study drug; and/or the adverse event abates or resolves upon discontinuation of the study drug or dose reduction and, if applicable, reappears upon re-challenge.
NO	An adverse event will be considered related, unless it fulfills the criteria specified below. Evidence exists that the adverse event has an etiology other than the study drug (e.g., preexisting medical condition, underlying disease, intercurrent illness, or concomitant medication); and/or the adverse event has no plausible temporal relationship to administration of the study drug (e.g., cancer diagnosed 2 days after first dose of study drug).

For patients receiving combination therapy, causality will be assessed individually for each protocol-mandated therapy.

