5.6 ADVERSE EVENTS THAT OCCUR AFTER THE ADVERSE EVENT REPORTING PERIOD

At the time of study treatment completion or study treatment discontinuation, the investigator should instruct each patient to report to the investigator any subsequent adverse events that the patient's personal physician believes could be related to prior study drug treatment or study procedures.

The Sponsor should be notified if the investigator becomes aware of any serious adverse event that occurs after the end of the adverse event reporting period (defined as 28 days after the last dose of study drug), if the event is believed to be related to prior study drug treatment. These events should be reported through use of the Adverse Event eCRF. However, if the EDC system is not available, the investigator should report these events directly to the Sponsor or its designee, either by faxing or by scanning and emailing the paper Clinical Trial Serious Adverse Event/Adverse Event of Special Interest Reporting Form using the fax number or email address provided to investigators.

5.7 EXPEDITED REPORTING TO HEALTH AUTHORITIES, INVESTIGATORS, INSTITUTIONAL REVIEW BOARDS, AND ETHICS COMMITTEES

The Sponsor will promptly evaluate all serious adverse events and adverse events of special interest against cumulative product experience to identify and expeditiously communicate possible new safety findings to investigators, IRBs, ECs, and applicable health authorities based on applicable legislation.

To determine reporting requirements for single adverse event cases, the Sponsor will assess the expectedness of these events using the following reference documents:

Drug	Document
Fulvestrant	Fulvestrant Summary of Product Characteristics
Venetoclax plus fulvestrant combination	Venetoclax Investigator's Brochure for solid tumour studies

The Sponsor will compare the severity of each event and the cumulative event frequency reported for the study with the severity and frequency reported in the applicable reference document.

Reporting requirements will also be based on the investigator's assessment of causality and seriousness, with allowance for upgrading by the Sponsor as needed.

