Appendix 1 Schedule of Activities (cont.)

- ^y Adverse events possibly related to study drug are to be recorded as well as any concomitant medications used in association with the event.
- ^z After informed consent has been obtained but prior to initiation of study drug, only serious adverse events caused by a protocol-mandated intervention (e.g., invasive procedures such as biopsies, discontinuation of medications) should be reported. After initiation of study drug, all adverse events will be reported through 28 days after the last dose of venetoclax or fulvestrant, whichever is later.
- ^{aa} *New anti-cancer therapy after study drug discontinuation should be reported once known.*

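### Second primary malignancies are promised close monitoring, but from 28 days after the last study drug dose they are recorded only if judged drug-related

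*Combined protocol and SAP*

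**What the plan says.** Section 5.1.1.6 reports that second primary malignancies have occurred in the venetoclax haematology programme, that a causal link has not been confirmed, and that the observed incidence was in line with the general population. It ends: "The second primary malignancies will be closely monitored in this study". It gives no duration, form or procedure.

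The collection rules that apply are these:

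- **During treatment and for 28 days after (5.3.1):** "all adverse events will be reported through 28 days after the last dose of study drug (venetoclax or fulvestrant, whichever is later".
- **After that (5.3.1):** "investigators should report any deaths, serious adverse events, or other adverse events of concern that are believed to be related to prior study drug treatment". The details are left to 5.6.
- **After that (5.6):** the sponsor is to be told of a serious event "if the event is believed to be related to prior study drug treatment".
- **Off-treatment and survival visits (Appendix 1, footnote y):** "Adverse events possibly related to study drug are to be recorded as well as any concomitant medications used in association with the event".
- **Events of special interest (5.2.3):** the list introduced by "Adverse events of special interest for this study are as follows" contains potential drug-induced liver injury, suspected transmission of an infectious agent, and tumor lysis syndrome. Second primary malignancy is not on it.
- **Analysis (6.5):** no summary of second primary malignancy is named.

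Follow-up continues well beyond the 28 days. Survival and new anti-cancer therapy are collected about every 3 months (4.6.1, Appendix 1), and the study ends "2 years after the last patient is enrolled" unless all patients have died or withdrawn, or the sponsor stops it, before then (3.3).

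**The concern.** Section 5.1.1.6 frames the risk as an incidence compared with a background rate. Such a comparison needs every case counted over a known time at risk. Under the rules above, every case is counted only up to day 28 after the last dose. Beyond that, a case enters the data only if someone believes it could be drug-related.

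That filter is applied in an open-label trial by people who know the arm. Causality is assessed separately for each drug (5.3.4), and attribution to venetoclax is possible in one arm only. Section 5.1.1.6 also tells sites that no link has been confirmed, which may lead some to answer no. A low or zero count late in follow-up could then reflect few cancers or few attributions, and the data could not tell the two apart. New anti-cancer therapy is still reported once known (footnote aa), but that records a treatment and not a diagnosis.

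**Working it through.** **1. The plan's own figures.** Study length: 18 months of enrolment + 24 months after the last patient + 28 days of screening (28/30.44 = 0.92 month) = 42.9 months, against about 43 stated in 3.3. Deaths at the primary analysis (1.4): 19/51 = 37.3%, 9/52 = 17.3%, 28/103 = 27.2%. All reproduce.

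**2. Patients are followed outside the window.** Section 1.4 gives 17 + 9 = 26 deaths more than 28 days after last dose, out of 28. That is 93%.

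**3. How much patient-time is outside.** The documents give no time on treatment, so this step rests on assumptions:

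- The share still on treatment at 24 weeks (168/30.44 = 5.52 months) equals the planned clinical benefit rate in 6.1: 40% or 60%. Time on treatment is exponential.
- Death is exponential, scaled to 17.3% or 37.3% dead at 9.89 months (the arm proportions and the median survival follow-up in 1.4).
- Administrative end is spread evenly over 24 to 42 months after randomization.

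Rates per month:

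- stopping treatment: λT = −ln(0.40)/5.52 = 0.166, or −ln(0.60)/5.52 = 0.0926
- death: λD = −ln(1 − 0.173)/9.89 = 0.0192, or −ln(1 − 0.373)/9.89 = 0.0472

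With a = 0.92 month and follow-up limit C:

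- mean follow-up F = (1 − e^(−λD·C))/λD
- mean time in the window W = (1 − e^(−λD·a))/λD + e^(−λD·a)·(1 − e^(−(λT+λD)(C−a)))/(λT+λD)
- share outside = 1 − W/F

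Example with C = 9.89, 40% on treatment and 17.3% dead: F = 9.01, W = 5.21, share outside = 1 − 5.21/9.01 = 42%.

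| On treatment at 24 wk | Dead at 9.89 mo | Full plan (C 24–42): W / F, outside | Primary analysis (C = 9.89): W / F, outside |
|---|---|---|---|
| 40% | 17.3% | 6.19 / 24.30, 74.5% | 5.21 / 9.01, 42.2% |
| 40% | 37.3% | 5.38 / 16.59, 67.6% | 4.73 / 7.90, 40.2% |
| 60% | 17.3% | 9.42 / 24.30, 61.3% | 6.48 / 9.01, 28.1% |
| 60% | 37.3% | 7.65 / 16.59, 53.9% | 5.80 / 7.90, 26.7% |

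**4. Sensitivity.** Over the full plan, the share outside falls below half only if about 65% to 71% or more are still treated at 24 weeks. At the primary analysis, it exceeds half only if fewer than about 26% to 29% are. The primary-analysis column gives every patient the same 9.89-month limit. Spreading that limit evenly over 6 to 24 months gives about 38% to 56% outside.

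**5. What complete capture could show.** Suppose no second cancer occurred in 51 venetoclax patients with 1 to 2 years at risk each (assumption; 51 to 102 patient-years). The one-sided 95% upper limit is −ln(0.05) = 3.00 events, or 3.00/102 = 2.9 to 3.00/51 = 5.9 per 100 patient-years.

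**The case against.** The strongest reply is that ordinary safety reporting is itself monitoring. Up to day 28 every new malignancy is a reportable adverse event. If serious, it reaches the sponsor within 24 hours and is among the data the Internal Monitoring Committee reviews about every 6 months (3.2). Section 5.1.1.6 promises no duration. This stands, and a reader who infers that no rule at all serves the commitment goes too far. What is missing is any rule beyond ordinary reporting.

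A reader might also infer that no second cancer can appear in the data after day 28, or that sites never ask. The documents do not support either. Related events remain reportable without an end date, and the adverse event row in Appendix 1 is marked at both the off-treatment and survival visits. The contact exists, but what is recorded there is filtered by causality.

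The causality default also counts against the concern: "An adverse event will be considered related, unless it fulfills the criteria specified below" (5.3.4). So it is not shown that sites would usually answer no. However, the same guidance allows no where another cause is evident, and 5.6 asks patients to report only those later events that their physician believes could be related. The default reduces the filter without removing it.

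Three further points hold:

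- The window runs from the later drug, so venetoclax patients who continue fulvestrant stay under full collection.
- Control-arm events can be attributed to fulvestrant, so that arm is not shut out.
- Late deaths and their causes were reported in 1.4, so a fatal second cancer could surface that way.

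Finally, 5.3.1 could be read as asking for all later deaths and serious events, with relatedness qualifying only the last item. But it defers to 5.6, which limits serious events to those believed related.

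**Conclusion.** The point holds as a gap between a stated safety commitment and the collection rules. After day 28 from the later study drug, a new cancer judged unrelated need not be recorded. Incidence by arm is therefore incomplete and depends on unblinded judgement.

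The extent is an estimate. About 54% to 75% of planned patient-time lies outside full collection, and about 27% to 42% at the primary analysis, if the planned clinical benefit rates stand in for the share treated at 24 weeks. It is tempting to say that most follow-up is lost. That is plausible for the full plan under these assumptions, but it is not a figure in the documents and is not established at the primary analysis.

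A reader might also infer that a safety signal is being missed. Nothing in the documents shows this. They give no background cancer rate, and even a complete zero count would exclude only rates above about 3 to 6 per 100 patient-years. The case for change is complete and unfiltered recording at low cost.

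**What to change.** - **5.3.1, 5.6 and Appendix 1 (footnote y):** require any new malignancy to be reported regardless of causality, in both arms, until end of study. Ask about it at the existing off-treatment visits and roughly 3-monthly survival contacts.
- **6.5:** tabulate new malignancies by arm over the whole follow-up. State that for patients already past the window or dead, capture is retrospective and may be incomplete.
- **Consistency:** bring the believed-related wording of 5.3.1 and 5.6 and the possibly-related wording of footnote y into line. Reconcile the 30-day reference in 5.4.2.2 with the 28 days used elsewhere.

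If the sponsor does not want all-cause capture, the minimum is to reword 5.1.1.6 so that it says complete collection ends at 28 days.

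The cost is one question at contacts already scheduled, one eCRF entry, one short table and a small site reporting burden. No visit or test is added. Because the current version follows the primary analysis, the change needs a further amendment (9.7) and some look-back at sites.
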